3.0 STUDY POPULATION

3.1 SELECTION OF THE STUDY POPULATION

1. For Aims 1, 2 and 3A, data for patients will be obtained from the Cedars-Sinai electronic medical record.
2. For Aim 3B, a sample of 10 patients seen in the Hypertension Center or Women’s Heart Center clinic, who meet the pre-defined criteria for uncontrolled hypertension at the time of data procurement, will be selected.
3. For Aim 4A, a sample of 20 patients seen in the Hypertension Center or Women’s Heart Center as well as 7 medical providers will be selected to inclusion in interview discussions.
4. For Aim 4B, a sample of 60 patients hypertensive patients taking antihypertension medications will be selected.

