The pilot RCT study would include 60 randomly selected hypertensive patients on hypertension treatment who may receive text message reminder and/or incentives, depending on the treatment group to which they are randomly assigned. Participants will be randomly assigned to one of three treatment groups: the control group (receives care as usual plus information on importance of establishing pill-taking routines), the message group (receives daily text messages for 3 months reinforcing information on importance of establishing pill-taking routines), or the incentive group (in addition to the same daily text messages as the message group, has a chance of winning small, intermittent rewards for taking medication in accordance with established pill-taking routine). The intervention period will last for 3 months and data monitoring will occur for an additional 6 months post-intervention totaling 9 months. Participants randomized into the incentive cohort will be eligible for a drawing only if they achieve greater than 80% medication adherence. The drawing will take place once a month for the first three months of participation with a chance to receive \$0, \$25, or \$50. Outcome measures include electronically measured medication adherence, hypertension control, adherence to established pill-taking routine, and feasibility and acceptability of intervention. We hypothesize that patients in the message and incentive groups will have higher medication adherence and hypertension control compared to the control group, and that patient in the incentive group will show greater adherence to established their pill-taking routine compared to the message and control groups.

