Behavioral Economics to improve Antihypertensive Therapy Adherence (BETA)

NCT04029883

Statistical Analysis Plan

February 21, 2023

[name] MS
Director of Clinical Analytics

Cedars-Sinai Medical Center
Smidt Heart Institute

We will determine acceptability and feasibility from participants' program experience described above and the focus groups in Phase 3. To estimate preliminary efficacy, we will perform statistical analyses comparing group-level differences in the primary and secondary outcome measures. We will use an Analysis of Covariance (ANCOVA) framework to test for group differences in each outcome at 3-month intervals, controlling for the client characteristics that are found to differentiate the groups at baseline. For analyses of dichotomous variables, such as hypertension control, we will use a non-parametric McNemar's test and an analogous multiple logistic regression to control for covariates to assess group differences. In addition to static comparisons of group means for each outcome at 3-month intervals, we will take advantage of the longitudinal nature of the data by using repeated measures and time-series techniques. Specifically, a linear mixed model with repeated observations will be fit using maximum likelihood through 'xtmixed' in the software package Stata in order to study group-level temporal dynamics in daily measures of the primary and secondary outcomes.

Specific Aim 2a: The overall impact between the pooled (*Message* group + *Incentive* group) compared to the *Control* group will be evaluated using both: 1) the comparison of group means and 2) a repeated observation regression framework that controls for observable differences between study groups and the correlation between observations of the primary and secondary outcomes for the same individual over time.

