Specific Aim 2b: The impact between the more intensive *Incentive* group compared to the lower-resource *Message* group will be evaluated using the same methods as above. Through this modeling framework we will utilize a range of variables. The independent variables in the above regression models will be used not only as control variables to improve efficiency but also to learn about the paths through which the intervention works and to identify subgroups that are likely to particularly benefit from the intervention. For example, by estimating regression models with and without measures of participants' intrinsic motivation as independent variables, we can study the mediating role of motivation on the formation of behavioral routines. The conceptual framework allows for additional mediators of behavior such as present bias, which may naturally hinder the capability of some participants to establish healthy routines. One additional method for testing this effect is to form an interaction between the present bias measure and the intervention indicator variable. With respect to the dependent variables, the primary and secondary outcomes are mean antihypertensive adherence and blood pressure control, with an exploratory focus on our quantified measure of adherence routinization. Continuous variables will be assessed for normality and transformed if needed. We will conduct analyses for the whole sample as well as separately by age and sex to better understand potential heterogeneous treatment effects. Logistic models will be estimated for binary outcome measures. We will also test whether routine adherence can be predicted based on observable characteristics; if so, in the subsequent R01 study the intervention may be targeted to those least likely to form healthy pill-taking routines on their own.

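### The SAP fits its mixed model by maximum likelihood with no small-sample correction: intervals are slightly too narrow for the main arm contrasts, and more so with covariates or in age and sex subsets

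*SAP*

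**What the plan says.** The analysis paragraph that opens the SAP first plans ANCOVA comparisons at 3-month intervals. It then adds a longitudinal model of the daily outcomes: "a linear mixed model with repeated observations will be fit using maximum likelihood". The fit is to be run "through 'xtmixed' in the software package Stata". It does not mention REML, a degrees-of-freedom method, a t reference or the random-effects structure.

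Under Specific Aim 2a, "The overall impact between the pooled (*Message* group + *Incentive* group) compared to the *Control* group" is to be assessed in two ways, by comparing group means and by a repeated-observation regression adjusted for observable group differences. The Specific Aim 2b paragraph states: "The impact between the more intensive *Incentive* group compared to the lower-resource *Message* group will be evaluated using the same methods as above". The same paragraph adds: "We will conduct analyses for the whole sample as well as separately by age and sex". It does not say which model the subset analyses use, how age is cut, or how many covariates enter.

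On size, Protocol section 4.0 states that "The pilot RCT study would include 60 randomly selected hypertensive patients" and that "Participants will be randomly assigned to one of three treatment groups". Section 3.1 gives the same total. No allocation ratio is stated. For Aim 4B, section 7.2 gives no alpha, power or target effect, and describes the work as pilot data for a later R01.

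**The concern.** Daily cap records add days, not people. A difference between arms is a difference between people, so its standard error depends mainly on the between-person variance, estimated from 60 participants or fewer. Maximum likelihood estimates that variance with divisor N instead of N minus the number of person-level coefficients. A normal reference then ignores the uncertainty in the estimate. Both effects narrow the interval, and both grow as covariates are added or the sample is split.

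At stake is the stated uncertainty around the preliminary efficacy results that will inform the R01. The SAP also wants to use its models to find subgroups that benefit most, and small subsets are where the understatement is largest.

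**Working it through.** The documents give no figure for this point, so there is nothing to reproduce first.

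**Inputs from the documents:** 60 participants and three groups (Protocol 3.1 and 4.0); maximum likelihood and xtmixed (SAP); contrasts 2a and 2b, and separate analyses by age and sex (SAP).

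**Assumptions:**
- equal allocation, 20 per arm, with no dropout
- two-sided 5% level
- normal reference for xtmixed
- balanced data with a correctly specified person random intercept
- subsets of half the sample
- none or five person-level covariates

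**Formula.** In this case the arm contrast is a regression on person means, with N people and p person-level coefficients. The exact statistic T follows t with N − p degrees of freedom. The maximum-likelihood standard error is too small by the factor √((N − p)/N), so a nominal 5% z test rejects when |T| > 1.96 × √((N − p)/N). Hence:

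- type I error = 2 × P(t(N−p) > 1.96 × √((N − p)/N))
- widening needed = t(0.975, N−p) / [1.96 × √((N − p)/N)] − 1

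**Worked examples.** For 2a, N = 60 and p = 2: √(58/60) = 0.983, the cut-off is 1.96 × 0.983 = 1.93, and the type I error is 5.9%. For 2b as a separate two-arm fit, N = 40 and p = 2: √(38/40) = 0.975, the cut-off is 1.91, and the type I error is 6.4%.

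| Setting | N | p | Cut-off | Type I error | Widening needed |
|---|---|---|---|---|---|
| 2a, no covariates | 60 | 2 | 1.93 | 5.9% | 3.9% |
| Three-arm model, no covariates | 60 | 3 | 1.91 | 6.1% | 4.8% |
| 2b, no covariates | 40 | 2 | 1.91 | 6.4% | 6.0% |
| 2a, five covariates | 60 | 8 | 1.82 | 7.4% | 10.0% |
| 2b, five covariates | 40 | 7 | 1.78 | 8.4% | 14.3% |
| 2a, half subset, no covariates | 30 | 2 | 1.89 | 6.9% | 8.2% |
| 2b, half subset, no covariates | 20 | 2 | 1.86 | 7.9% | 13.0% |
| 2a, half subset, five covariates | 30 | 8 | 1.68 | 10.7% | 23.6% |
| 2b, half subset, five covariates | 20 | 7 | 1.58 | 13.8% | 36.7% |

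The five-covariate rows for 2a use three-arm coding (3 + 5 = 8). With the two active arms pooled into one indicator (p = 7), they become 7.1% (N = 60) and 10.0% (N = 30).

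**Without the normal-reference assumption.** If a t reference were used with maximum likelihood, widths would still be √((N − p)/N) of the REML widths: 0.983 for 2a and 0.975 for 2b. Type I error would be 5.4% and 5.6%.

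**Simulation check.** Maximum-likelihood fits with z intervals (nine time points, 1,500 runs per setting) of a three-arm model gave coverage of 94.1%, 92.3% and 88.1% at 20, 10 and 5 per arm, with Monte Carlo standard error of 0.6 to 0.8 points. The closed form with p = 3 gives 93.9%, 92.6% and 89.5%. In a separate simulation of 8,000 trials per setting, REML with a t reference brought type I error back to 4.7 to 5.4%.

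**The case against.** The strongest reply is that the SAP does not rely on this model alone. ANCOVA is named first, already uses t-based inference on one value per person, and serves 2a and 2b equally. That stands. A reader might infer that both aims are read only from the mixed model, but the SAP makes it one of two routes and introduces it mainly to study change over time.

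Second, the effect on the main contrasts is about one percentage point of type I error. That also stands. The pilot sets no alpha or decision rule, and in the balanced case REML and maximum likelihood give the same point estimate. A reader might infer that the effect estimate passed to the R01 is biased. In that case it is not; only its stated precision is.

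Third, the larger figures stack assumptions. The 10.7% and 13.8% need an even split, five covariates in each half, and the mixed model run within subsets, none of which the SAP specifies. Without covariates the same subsets give 6.9% and 7.9%. So the larger figures are illustrations, not properties of the plan. Still, the SAP leaves the covariate list open, and its wish to explore motivation, present bias and an interaction makes several coefficients plausible.

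Fourth, the normal reference is inferred from the command name, and 20 per arm from equal allocation. Both are assumptions, but the maximum-likelihood bias remains without the first, and dropout would make matters worse.

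Finally, a reader might infer a much larger error in group-by-time tests, since a random-intercept-only model treats each person's many days as independent information on slope. The SAP does not say that only an intercept will be fitted, and it promises to handle within-person correlation. The error would also depend on between-person slope variation that the documents do not give. The random-effects structure should be stated, but no headline figure is warranted.

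**Conclusion.** The point holds as a minor correction for the main contrasts and a more material one for adjusted and subset analyses. As written, the mixed-model intervals are too narrow: they need to be about 4 to 6% wider for the unadjusted whole-sample contrasts, where type I error is 5.9 to 6.4% instead of 5%. With five covariates it is 7.4 to 8.4%. In half-sample subsets, if this model is used there, it is about 7 to 8% without covariates and 11 to 14% with five.

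The direction follows from the SAP's stated estimator. The sizes rest on the assumptions listed with the calculation.

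**What to change.** In the SAP's analysis paragraph, replace maximum likelihood in xtmixed with REML and Kenward-Roger or Satterthwaite degrees of freedom (in Stata, `mixed` with `reml dfmethod(kroger)`). State the random-effects structure: a person random intercept, plus a person random slope for any group-by-time claim. Say which model the age and sex analyses use, and label their intervals exploratory.

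The cost is a few lines in the SAP, with the same software and no new data. The price is the extra interval width shown in the table: modest for the unadjusted whole sample, 10 to 14% with five covariates, and up to about 24 to 37% in half subsets with five covariates. That added width is the uncertainty the present method leaves out.

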	Patient reason for missing or absent blood pressure data, if applicable

*Note, baseline demographic factors for patients enrolled in Aim 3B will already have been collected as part of Aim 1.

Table 4 (Data collected for Aim 4B only)

Survey measures (initial visit, month 3 visit, month 9 visit)	Behavior economic measurements (biases, behavioral automaticity, intrinsic motivation measures)
	Demographic and socioeconomic data (age, gender, education, employment, insurance type, income, marital status and housing)
	Medical factors (baseline blood pressure, number of non-antihypertensive medications on at baseline, final number of antihypertensive medications at the end of the study and history of cardiovascular disease)
	Physical symptoms/side effects of medications
	Structural barriers to medication adherence (insurance status, patient distance to pharmacy)
MEMS-cap electronic data (automatically captured)	Date of bottle opening (for hypertensive medication)
	Time of bottle opening (for hypertensive medication)

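### Present bias is called a mediator, but the only test named for it is a treatment interaction, which addresses effect modification

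*SAP*

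**What the plan says.** SAP, Specific Aim 2b, gives the independent variables in its regression models two explanatory purposes: "to learn about the paths through which the intervention works and to identify subgroups that are likely to particularly benefit from the intervention". The first is a question about mechanism, the second about effect modification.

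For mechanism, its worked example is intrinsic motivation: "by estimating regression models with and without measures of participants' intrinsic motivation as independent variables, we can study the mediating role of motivation". It then adds present bias to the list of mediators: "additional mediators of behavior such as present bias, which may naturally hinder the capability of some participants to establish healthy routines". The next sentence gives the test: "One additional method for testing this effect is to form an interaction between the present bias measure and the intervention indicator variable".

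The SAP does not say which visit's measurement enters either analysis. Protocol Section 5.4, Table 4, lists "Behavior economic measurements (biases, behavioral automaticity, intrinsic motivation measures") in a block headed "Survey measures (initial visit, month 3 visit, month 9 visit"). On the status of the outcomes, the SAP says that "the primary and secondary outcomes are mean antihypertensive adherence and blood pressure control, with an exploratory focus on our quantified measure of adherence routinization".

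**The concern.** A mediator lies on the path from treatment to outcome: the intervention changes it, and that change moves the outcome. An effect modifier is a characteristic across whose levels the treatment effect differs. A treatment-by-covariate interaction addresses the second question. In the SAP the effect to be tested is, on a plain reading, the mediating role just described, so the label and the test do not match.

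What is at stake is how a pilot finding is understood. If present bias modifies the effect, it says who responds. If it mediates the effect, it is something the intervention changes. These lead to different designs for the follow-on study that the pilot is meant to inform (Protocol Section 7.2). As written, a reader cannot tell which question the present-bias analysis will answer.

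**Working it through.** The documents give no figure for this analysis, and no alpha, power or effect size for Aim 4B, so there is nothing to reproduce. The check is on the logic, with a simulation as illustration.

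**1. The two roles in a linear model.** Let T be randomised treatment, M present bias and Y the outcome.

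- Pure mediation: M = aT + e1 and Y = bM + e2. The indirect effect is a × b. The coefficient of T × M in the model for Y is 0.
- Pure moderation: M is independent of T, and Y = cT + dTM + e. The T × M coefficient is d. Because a = 0, the indirect effect is 0.

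**2. Simulation.** Assumed values are a = b = c = d = 0.8, residual SD 1, and two-sided 0.05. Group sizes are 20 vs 20 (Aim 2b) and 40 vs 20 (the pooled Aim 2a comparison). Both take the 60 patients of Protocol Section 3.1 as three equal arms, which is an assumption because no allocation ratio is stated. A 2,000 vs 2,000 case shows what happens when size is no limit. There were 10,000 runs for each of the two small sizes and 1,000 for the large one. The true indirect effect under mediation is 0.8 × 0.8 = 0.64. In the third scenario treatment has an effect of 0.8 and M plays no part.

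| Truth | Groups | Interaction rejects | Mean change in T coefficient when M is added | Joint-significance mediation test rejects |
|---|---|---|---|---|
| Mediation | 20 vs 20 | 5.2% | 0.643 | 69.7% |
| Mediation | 40 vs 20 | 5.0% | 0.638 | 81.6% |
| Mediation | 2,000 vs 2,000 | 3.6% | 0.640 | 100% |
| Moderation | 20 vs 20 | 64.0% | -0.003 | 2.8% |
| Moderation | 40 vs 20 | 77.0% | -0.002 | 4.9% |
| Moderation | 2,000 vs 2,000 | 100% | -0.001 | 5.4% |
| Neither | 20 vs 20 | 4.8% | 0.000 | 0.2% |
| Neither | 40 vs 20 | 4.8% | 0.000 | 0.2% |
| Neither | 2,000 vs 2,000 | 5.6% | 0.000 | 0.1% |

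The change column is the absolute reduction in the T coefficient. Under pure mediation the interaction test stays near its nominal level at every size. Under pure moderation it rejects often although nothing is mediated. The comparison of models with and without M recovers the indirect effect in the linear case.

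**3. Timing.** A value measured before randomisation cannot be changed by treatment and so cannot mediate its effect. A mediation analysis needs a value taken after randomisation and before the outcome. Month 3 could serve, because monitoring runs for six months after the three-month intervention (Protocol Section 4.0). Table 4 suggests a month-3 value but does not establish it. The same block holds items that cannot recur at all three visits, such as baseline blood pressure and the final count of antihypertensive drugs, and it refers to biases without naming present bias.

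**4. Precision.** For a plain difference in means at 80% power and two-sided 0.05, with equal arms and no dropout, the detectable difference is (1.960 + 0.842) × sqrt(1/n1 + 1/n2):

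- 20 vs 20: 2.802 × sqrt(0.100) = 0.89 SD
- 40 vs 20: 2.802 × sqrt(0.075) = 0.77 SD

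The pilot can detect only large main effects, so interaction and indirect-effect estimates should be expected to be imprecise.

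**The case against.** The strongest reply is that the SAP does not rest the mechanism question on the interaction. It offers the interaction as an additional method, after the comparison of models with and without the variable, which is a recognised mediation check. This stands in part. A reader might infer that the whole mechanism question would be answered with the wrong analysis, and the SAP does not support that. However, the with/without comparison is spelled out only for motivation, and its extension to present bias is left to inference. In the logistic models planned for binary outcomes, adding a covariate can also shift the treatment coefficient without any mediation.

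A second reply is that the interaction is the right tool for the subgroup purpose in the same section. Present bias is described as a natural hindrance for some participants, which is how one describes a pre-existing trait. A mediator of behavior is also not plainly a mediator of the treatment effect. This stands: the error may lie in the label and not in the test, and the fix keeps the test.

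Three further inferences are tempting but go beyond the documents:

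- That a significant interaction would be reported as mediation. The SAP has no reporting rule, so this is a risk only.
- That the follow-on study would be aimed at the wrong target. The SAP's one statement on targeting concerns choosing patients by observable characteristics that predict routine adherence. It does not depend on this interaction.
- That interaction and mediation are unrelated in general. The simulation covers only pure cases. Causal mediation models can include a treatment-by-mediator term, so such a term is not misplaced in itself.

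**Conclusion.** The point holds in limited form. The SAP gives present bias a mediating role, and the only test it names specifically for present bias addresses effect modification. That interaction alone cannot support or refute mediation.

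The severity is low. The mechanism analysis concerns routine formation, which the SAP treats as exploratory, in a 60-patient pilot. The primary and secondary group comparisons are not affected. The algebra assumes linear models and pure cases. The simulated percentages also depend on the assumed 0.8 SD paths and equal arms, so they illustrate the direction of the problem and do not predict this trial's results.

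**What to change.** In SAP Specific Aim 2b:

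1. Describe present bias as a potential effect modifier. Enter its baseline value in the interaction, confirming that the initial-visit survey is completed before assignment, and report the result as effect modification.
2. State which visit's measurement each model uses.
3. Make a mediation claim for present bias or motivation only from a post-randomisation value measured before the outcome. That means month 3, if confirmed as collected, with adherence after month 3 as the outcome. Estimate the indirect effect with a bootstrap interval, state the assumption of no unmeasured mediator-outcome confounding, and label the analysis exploratory.

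The cost is a few sentences in the SAP and one extra exploratory analysis that will be imprecise at this size. That analysis would speak to adherence after the intervention period and not during it. If month-3 present bias is not collected, item 3 cannot be done for present bias, and items 1 and 2 are enough.

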5.4 SOURCE DOCUMENTS

- For Aims 1, 2 and 3A, we seek to obtain the data in Tables 1 and 2 from the EMR with the assistance of the Research and Informatics Scientific Computing Core (RISCC)
 - Table 1 contains patient level data to be obtained at the visit level
 - Table 2 contains medications to be obtained at the patient level for each visit. Data is to include if the medication has been prescribed and if so, at what dose and frequency. The prescribing provider and providers specialty will also be acquired.
 - Zip Code will be used to estimate population level sociodemographic factors from census data
- For Aim 3B, patient medical records will be the source document for the information identified in Tables 1 and 2, as well as information outlined in Table 3
- For Aim 4B, survey instruments will be the source document for the variables outlined in Table 4. Video diaries will be obtained and stored, as detailed in section 5.5.

Table 1 (Data collected for all aims)

Blood Pressure readings at each outpatient clinic visit
Provider Name at each visit
Provider Specialty at each visit
Provider demographic
ICD-9/ICD-10 codes
Dates of each clinic visit
Patient insurance information
Patient date of birth
Patient ZIP Code
Patient age
Patient gender
Patient ethnicity
Patient BMI at each visit
Primary Care Physician Name and Practice Location
Patient glomerular filtration rate at each clinic visit
Highest A1C level during study period

Table 2 (Data collected for all aims)

ACE-Inhibitors/Angiotensin Receptor Blockers	Beta-Blockers	Diuretics	Calcium Channel Blockers	Nitrates	Other
Lisinopril	Metoprolol	Hydrochlorothiazide	Amlodipine	Imdur	Hydralazine
Benazepril	Bisporolol	Chlorthalidone	Diltiazem	Isordil	Clonidine

Captopril	Carvedilol	Metolazone	Verapamil		Aliskiren
Enalapril	Propranolol	Lasix	Felodipine		
Fosinopril	Nadolol		Isradipine		
Ramipril	Atenolol		Nifedipine		
Perinodopril	Labetalol				
Losartan	Nebivolol				
Valsartan					
Candesartan					
Irbesartan					
Telmisartan					
Azilsartan					
Eprosartan					
Olmesartan					

Table 3 (Data collected for Aim 3B only)

Initial Visit (Week 0)	Baseline blood pressure
	Current medications (names, doses and frequencies)
	Laboratory values (basic metabolic panel, TSH and A1C)
Weekly Phone Call (Weeks 1-8)	Record all uploaded blood pressures in the EMR
	New/updated laboratory values
	Current medications (names, doses and frequencies)
	Changes to medications (names, doses and frequencies)

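### The Aim 4B trial names blood pressure control (yes/no) as its only blood pressure outcome; adding numeric pressure adjusted for baseline would give the R01 more precise estimates

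*SAP*

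**What the plan says.** The SAP, under Specific Aim 2b, states that "the primary and secondary outcomes are mean antihypertensive adherence and blood pressure control". Its general analysis paragraph sets the scale of the second of these: "For analyses of dichotomous variables, such as hypertension control", it prescribes McNemar's test and a multiple logistic regression. The protocol agrees. Sections 4.0 and 7.1 name hypertension control for Aim 4B, and neither names a numeric pressure.

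On covariates, the SAP adjusts for characteristics found to differ between the groups at baseline. Baseline pressure is not named, so it would enter only if it met that condition.

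On data, protocol Section 5.3 sends Aim 4B to Table 4, which lists "Medical factors (baseline blood pressure, number of non-antihypertensive medications on at baseline" and other items but no follow-up pressure. Table 1, headed as applying to all aims, lists "Blood Pressure readings at each outpatient clinic visit".

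On design, Section 3.1 states: "For Aim 4B, a sample of 60 patients hypertensive patients taking antihypertension medications will be selected". Section 4.0 adds: "Participants will be randomly assigned to one of three treatment groups". The SAP's two contrasts are "The overall impact between the pooled (*Message* group + *Incentive* group) compared to the *Control* group" (Specific Aim 2a) and "The impact between the more intensive *Incentive* group compared to the lower-resource *Message* group" (Specific Aim 2b).

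**The concern.** A cut at 130/80 ignores all movement on either side of it. A participant far above goal can improve substantially and still count as not controlled. With 60 patients in three groups, there is little information to spare.

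Section 7.2 gives the purpose of Aims 4A and 4B as pilot data for a future R01, so the useful product is an effect estimate and its standard error. Blood pressure is also the clinical efficacy outcome that does not come from the bottle cap, which makes its precision worth protecting. The numeric value has to be measured anyway to decide whether a participant is controlled.

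**Working it through.** **Inputs from the documents.** 60 patients in three groups; contrasts of pooled active groups against control, and Incentive against Message; control defined as below 130/80 (protocol Section 4.0, written for the record-based aims and not restated for Aim 4B). The only control rate available is the national figure of about one half in Section 1.0. There is no power calculation for Aim 4B to reproduce.

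**Assumptions.** Equal allocation (20 per group, so 40 against 20 for the pooled contrast), two-sided alpha 0.05, no dropout, roughly normal pressure, and an intervention that shifts the mean. The control rate p is varied from 20% to 80%.

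**Step 1: information kept by the split.** Let the intervention shift pressure by a small d, in SD units. Comparing means carries information proportional to d². The proportion controlled moves by about φ(z_p)·d with variance p(1−p), so the ratio of the two is

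E = φ(z_p)² / [p(1−p)].

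- p = 50%: 0.399² / 0.25 = 0.637. Loss 36%; 60 patients are worth 60 × 0.637 ≈ 38.
- p = 30% or 70%: E = 0.576. Loss 42%; about 35 patients.
- p = 20% or 80%: 0.280² / 0.16 = 0.490. Loss 51%; about 29 patients.
- p = 10% or 90%: E = 0.342. Loss 66%.

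**Step 2: the joint criterion.** Control requires both systolic below 130 and diastolic below 80. Take bivariate normal pressures with assumed SDs of 16 and 10 mmHg, correlation 0.5 or 0.65, and a diastolic shift of 0.4 or 0.6 times the systolic shift. At control rates of about 20% to 56%, the joint yes/no outcome keeps 0.433 to 0.725 of the information in systolic pressure alone. The loss is about 28% to 57%.

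**Step 3: baseline pressure.** Adjusting the numeric value for baseline multiplies its residual variance by 1 − r². Unadjusted yes/no against baseline-adjusted mean therefore keeps E × (1 − r²). With an assumed r = 0.5 this is 0.637 × 0.75 = 0.48 at p = 50% (loss 52%) and 0.490 × 0.75 = 0.37 at p = 20% or 80% (loss 63%). These losses combine the split with the missing covariate.

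**Step 4: power in the pooled contrast (40 against 20), control-group rate 50%.**

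| True shift | Mean, unadjusted | Mean, adjusted (r = 0.5) | Yes/no, unadjusted |
|---|---|---|---|
| 0.3 SD | 19% | 24% | 14% |
| 0.5 SD | 45% | 56% | 31% |
| 0.8 SD | 83% | 92% | 62% |

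The shift detectable with 80% power is 0.77 SD for the mean, 0.66 SD with baseline adjustment, and about 1.01 SD for yes/no (control rising from 50% to 84%).

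**Step 5: like for like, both analyses adjusted for baseline.** Simulated systolic pressure, assumed SD 15, r = 0.5:

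- 8 mmHg: about 56–57% power for ANCOVA against 37–40% for logistic regression.
- 4 mmHg: about 20% against 13%.
- 3 mmHg: about 12–14% against 9–10%.

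The relative loss persists at small effects, but the gap in power narrows to a few points.

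**The case against.** **The SAP may already cover numeric pressure.** It applies ANCOVA to each outcome and a linear mixed model to daily measures of the primary and secondary outcomes, methods that suit a continuous variable. But these sentences name no numeric pressure, hypertension control is expressly placed among the dichotomous variables, and protocol Section 5.2 schedules monthly and then three-monthly data, not daily pressure. If numeric pressure was intended, the SAP should say so, and the fix is the same.

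**Control is the pre-specified hypothesis, in a pilot without a power target.** This stands. It argues for adding the numeric analysis beside control, not for demoting control. It also means that no stated power claim is missed.

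**The sizes rest on outside assumptions.** This stands too. SD, effect, correlation, allocation and control rate are all assumed, and Step 5 shows that neither analysis is powerful if the effect is small.

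**The readings may not be there.** In part. Table 4 lists only baseline pressure, and follow-up readings rest on the all-aims heading of Table 1. Some follow-up reading is needed to derive control, but the plan does not say that each participant has one at months 3 and 9.

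**Stronger readings that the documents do not support.** A reader might infer that participants already controlled at entry are certain to be enrolled and cannot improve on the yes/no scale. Sections 3.2 and 3.4 set no pressure threshold for Aim 4B, but Section 2.0 describes the sample as uncontrolled; the point arises only under the former. A reader might also infer that blood pressure is the only trial outcome not derived from the bottle cap. Section 4.0 also lists feasibility and acceptability, so the claim holds only for clinical efficacy.

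**Conclusion.** The point holds as a cheap improvement. The plan names a single, dichotomous blood pressure outcome and does not fix baseline pressure as a covariate. The split costs about 36% of the information at a 50% control rate, about 51% at 20% or 80%, and roughly 28% to 57% for the joint criterion, given approximate normality and a mean shift. The loss affects blood pressure only; adherence is analysed as a mean. The consequence is less precise estimates for the R01. It would be wrong to conclude that numeric pressure makes the trial adequately powered: at an assumed 4 mmHg, power is about 20% against 13%.

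**What to change.** 1. In the SAP, add follow-up systolic and diastolic pressure at months 3 and 9 as numeric outcomes, compared between groups by ANCOVA with baseline pressure as a fixed covariate, whether or not the groups differ on it.
2. Keep control below 130/80 as the pre-specified binary outcome, state that this cut applies to Aim 4B, and adjust the logistic model for baseline pressure as well.
3. State in protocol Table 4 that pressure at the follow-up visits is recorded for Aim 4B.
4. Reconcile Section 2.0 (uncontrolled patients) with Sections 3.2 and 3.4 (no pressure threshold).

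Cost: SAP and table wording, and one more secondary analysis to report. No new measurement is needed provided that the visit readings used to derive control are kept as numbers.
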